9.5.1. Sensitivity Analyses of the Primary Efficacy Results

Select sensitivity analyses may be performed on the primary efficacy results if there is missing data or protocol deviations that can impact results.

9.6. Analysis of the Secondary Efficacy Endpoints

T25FW and 9-HPT

Secondary efficacy endpoints are listed in [Section 3.2.2](#). This section provides additional details.

In addition to the primary efficacy endpoint evaluated at Week 28, the percentage of subjects with improvements from baseline to each post baseline timepoint in either T25FW or 9-HPT of $\geq 15\%$, $\geq 20\%$ and $\geq 30\%$ will also be evaluated.

Other thresholds may be considered to define responder analyses for the efficacy endpoints if the above are deemed to be too low or too high.

As indicated in [Section 3.2.2](#), in addition to determining if a subject was a responder on either T25W or 9-HPT at each timepoint, these two efficacy assessments will be separately evaluated at each timepoint to see improvements in each of them.

- Percentage of subjects who improve on T25FW by $\geq 25\%$ (Other thresholds such as $\geq 15\%$, $\geq 20\%$ and $\geq 30\%$ will also be evaluated)
- Percentage of subjects who improve on 9-HPT by $\geq 25\%$ (Other thresholds such as $\geq 15\%$, $\geq 20\%$ and $\geq 30\%$ will also be evaluated)

In order to determine the amount of change or % change from baseline to each post baseline timepoint, mean changes in T25FW from baseline to each post baseline timepoint will be summarized in addition to other descriptive statistics for continuous variables. This will be repeated for the 9-HPT. In addition, mean changes in feet per second will be summarized as noted above for the timed walk.

Biomarkers

CSF and/or serum samples will be collected for determining the concentration of neurotropic factors, inflammatory markers, miRNA, etc. collectively referred to as biomarkers.

Details of biomarker analyses will be specified subsequently.

Biomarkers to be assessed include the following:

Biomarker Type	CSF	Serum
MSC-NTF derived Neurotropic Factors	BDNF, GDNF, HGF, LIF, VEGF, TSG-6, G-CSF	BDNF, GDNF, HGF, LIF, VEGF, TSG-6, G-CSF
Inflammatory Biomarkers	MCP-1, SDF-1, CHIT-1, TNF- α , sCD27 and a full panel of cytokines, chemokines and regulatory proteins	Full panel of cytokines, chemokines and regulatory proteins
miRNA	miRNA panel	miRNA panel
Neurodegeneration	NfL, NfH, GFAP	NfL, NfH, GFAP

Expanded Disability Status Scale (EDSS)

Mean Changes and % Changes from baseline to each post baseline time point in EDSS Scores will be summarized along with other descriptive statistics for continuous variables.

In addition Subjects that improve on EDSS by ≥ 1.0 for those with baseline EDSS ≤ 5.5 and improvement ≥ 0.5 for those with baseline EDSS > 5.5 (Note maximum EDSS for subjects enrolled is 6.5) between baseline and each post baseline time point will be summarized. The EDSS is a 10 point scale with half point increments. Other thresholds for improvements may also be explored.

A shift Table will summarize changes in each of the FS subscales (Pyramidal, Cerebellar, Brainstem, Sensory, Bowel and Bladder, Visual, Cerebral or Mental, and Ambulation) from baseline to each post-baseline timepoint. EDSS is widely used as an outcome measure in MS. A 1.0-point change in the EDSS (for those with baseline EDSS ≤ 5.5) or 0.5-point change in EDSS (for those with baseline EDSS > 5.5) are considered clinically meaningful⁵.

The EDSS is an objective approach to quantify the level of physical disability in MS. It provides a total score on a scale that ranges from 0 (no disability) through 1 to 10 (death due to MS) in 0.5-point steps. The first levels 1.0 to 4.5 refer to people with a high degree of ambulatory ability and the subsequent levels 5.0 to 9.5 refer to the loss of ambulatory ability.

In addition, it also provides eight subscale measurements called FS scores. The levels of function within each category refer to the eight FSs affected by MS: Pyramidal (motor function) (P); Cerebellar (C11); Brainstem (BS); Sensory (S); Bowel and Bladder (BB); Visual (V); Cerebral or Mental (Cb); Ambulation.

For additional detail see [Protocol, Sections 15.2.4](#) in Appendix 1.

Multiple Sclerosis Walking Scale (MSWS-12)

Mean Changes and % Changes from baseline to each post baseline timepoint in MSWS-12 Scores will be summarized along with other descriptive statistics for continuous variables.

Percentage of Subjects that improve on MSWS-12 Scores by ≥ 8 points between baseline and each post baseline time point. A 7 point change in MSWS-12 is considered clinically meaningful⁹. Other thresholds such as improvements of ≥ 7 , ≥ 9 points will also be presented.

The MSWS-12 is a patient-reported outcome measure of the walking limitations due to MS during the past 2 weeks. It contains 12 questions that assess the impact of MS on different aspects of walking function and quality.

Total administration time should be approximately 5 minutes. Activities are rated by participant from 1 (not at all) to 5 (extremely) and summed to calculate a total score using a scale from 0 to 60 (ranging from low to high impact on walking). This score is then divided by 60 and multiplied by 100 to get a score between 0 and 100.

If a subject completes at least 6 items out of 12, the score is considered valid, otherwise if less than 6 items are completed the total score is considered missing.

If a subject does not complete all 12 items but does complete at least 6 items their total score is divided by the maximum score for the items completed and multiplied by 100.

Physical Activity as Measured by ActiGraph's CenterPoint Insight Watch (CPIW)

ActiGraph's CPIW (Wrist Sensor) is a medical-grade wearable physical activity, mobility, and sleep behavior monitoring FDA 510(k) cleared Class II medical device used for clinical research.

It will be issued to eligible subjects at Visit 1 with instructions on its use. The device is to be worn on the wrist of the non-dominant hand, throughout the duration of the study. The device will be returned to the site at Visit 7, the final study visit.

Subjects have the option to either take it off while they sleep or keep it on. It is water resistant so may be worn during showering.

The device contains an accelerometer and measures movements on the X, Y and Z coordinates.

These are then converted to various measures of physical activity, mobility and sleep quality. The device will allow to measure changes in mobility and physical activity following each treatment.

Analysis will include changes and % changes from baseline to each post baseline timepoint as well as between prior to each treatment and each week following it. Due to outliers, analyses may be performed including and excluding outliers.

Baseline will be the average of valid data from up to 7 days prior to the first treatment (V3), excluding the day of treatment.

Pre-treatment assessments will be the average of valid data from up to 7 days prior to the second (V4) and third treatments (V5), excluding the days of treatment.

Post treatment assessments will be based upon the average of valid data from each 7-day interval following each treatment visit (not including the day of visit).

A daily assessment will be considered valid if the device was worn for at least 4 hours. Data from valid days of assessments will be scaled by taking the level of activity, dividing it by the number of hours the device was worn while awake and multiplying it by 16 (average waking period).

- Analyses will summarize mean changes and % changes and other descriptive statistics for continuous variables from baseline to each post baseline week in Daily step count averaged over valid data during 7 days as indicated above
- Count per minute of daily activity averaged over valid data during 7 days as indicated above

Mean changes and % changes and other descriptive statistics for continuous variables in Daily Step Count from baseline to each successive T25FW

Improvements will also be evaluated by the following categorical analyses:

- Shift Table on time spent in each of the following categories: (Sedentary, Light, Lifestyle, Moderate, Vigorous, Very Vigorous)
- Percentage of time spent in light to vigorous physical activity based on a threshold of > 100 activity counts per minute

Additional analyses using data collected and derived from the Center Point Insight Watch including improvements in sleep quality may be performed.

Low Contrast Letter Acuity (LCLA)

Mean Changes and % Changes from baseline to each post baseline timepoint in LCLA Scores will be summarized along with other descriptive statistics for continuous variables. The LCLA score is an integer between 0 and 70 and indicates the correct number of letters identified.

The scores are recorded for the right eye, left eye and both eyes combined. These will be analyzed for the three settings 100%, 2.5% and 1.5%.

Additional categorical analyses will summarize the number and percentage of subjects with an improvement (increase) in LCLA score by ≥ 7 letters. A 7 letter change in LCLA is considered clinically meaningful⁸. Other thresholds such as improvements of ≥ 6 , ≥ 8 letters will also be presented.

Sloan LCLA charts are administered binocularly or each eye can be tested individually. The charts are placed on a retro-illuminated cabinet, eliminating the need for standardized room lighting, or on the wall in front of the participant. Participants are seated 2 m away and asked to read the letters aloud proceeding top to bottom and from left to right until they can no longer see the letters.

Total administration time, for a typical MS patient, is approximately 10–15 minutes to complete, when testing each eye individually and binocular vision for two different contrast levels. The

score for each chart is quantified as the number of letters identified correctly with a maximum score of 70 letters.

Symbol Digit Modalities Test (SDMT)

Mean Changes and % Changes from baseline to each post baseline timepoint in SDMT Scores will be summarized along with other descriptive statistics for continuous variables.

Additional categorical analyses will summarize the number and percentage of subjects with an increase in SDMT scores by ≥ 4 points. A 4 point change in SDMT is considered clinically meaningful⁷. Other thresholds such as improvements of ≥ 3 , ≥ 5 points will also be presented.

The SDMT involves a simple substitution task that normal children and adults can easily perform. Using a reference key, the examinee has 90 seconds to pair specific numbers with given geometric figures.

Total administration time should be approximately 5 minutes.

MSFC Composite Score

Two composite scores will be computed for the MSFC. One composite will include the T25FW, 9-HPT and SDMT and a second composite will include the T25FW, 9-HPT, SDMT and LCLA.

The MSFC Composite Score in the first case is computed as follows:

$$\text{MSFC Score} = \{(\text{Average (1/9-HPT)} - \text{Baseline Mean (1/9-HPT)} / \text{Baseline Std Dev (1/9-HPT)} \\ + \{ - (\text{Average 25-Foot Walk} - \text{Baseline Mean 25-Foot Walk}) / \text{Baseline Std-Dev 25-Foot Walk} \\ + (\text{SDMT} - \text{Baseline Mean SDMT}) / \text{Baseline Std Dev SDMT} \} / 3.0$$

Note: “Average (1/9-HPT)” is the average of the inverse (reciprocal) for the mean time of the two trials on the right hand and reciprocal of the mean time of the two left-hand trials from the test patient, Baseline Mean (1/9-HPT) and Std Dev (1/9-HPT) are the baseline values from each patient in all study groups combined at the baseline assessment;

“Average 25-Foot Walk” is the mean time from the two trials of the 25-foot timed walk; and we take the negative value of the Z-score to make the direction of change the same as the other components. Similarly, the Baseline Mean and Std Dev 25-Foot Walk are of all Baseline Groups combined;

and “SDMT” is the score from the test patient, and the Baseline Mean SDMT and Std Dev SDMT of the combined baseline assessments.

If a participant could not use one hand at the outset and could use it subsequently, a baseline value of the worst occurring 9HPT in the same either dominant or nondominant arm will be used to impute the baseline value.

A similar approach is used for second composite with all 4 elements of the MSFC.

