15.2.5. Multiple Sclerosis Walking Scale (MSWS-12)

The MSWS-12 is a patient-reported outcome measure of the walking limitations due to MS during the past 2 weeks. It contains 12 questions that assess the impact of MS on different aspects of walking function and quality.

Total administration time should be approximately 5 minutes. Activities are rated by participant from 1 (not at all) to 5 (extremely) and summed to calculate a total score using a scale from 0 to 100 (ranging from low to high impact on walking).

Brainstorm Cell Therapeutics Ltd.	IND#018615	
Phase 2 Clinical Protocol BCT-101-US Amendment 1.1, June 2019	MSC-NTF cells (NurOwn®)	Page 58 of 59

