6.7.3. Change from Baseline

Change from baseline is calculated as (post-baseline result – baseline result).

Percent change from baseline is calculated as (change from baseline/baseline result)*100 as long as baseline is non-zero. If baseline is 0, change from baseline is defined as missing.

If either the baseline or the post-baseline result is missing, the change from baseline and/or percentage change from baseline is set to missing as well.

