5.2 Multiple Sclerosis Walking Scale (MSWS-12)

The SAP indicated that MSWS-12 would be summarized using raw scores (0-60) as well as scores mapped to a 0-100 scale. Upon further review of the literature it was noted that the data are always presented on a 0-100 scale so no tabulations will be generated on the raw scores. The raw scores will be included in the data listings. MSWS-12 on scores mapped to a 0-100 scale will be summarized for following point improvement- ≥ 10 , ≥ 15 and ≥ 20 as is done in various publications.

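### The SAP's MSWS-12 formula yields scores from 20 to 100, not 0 to 100, so every change shrinks to 80% and the responder bars are higher than they appear

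*SAP*

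**What the plan says.** SAP 9.6 describes a 12-question instrument and gives the item coding as "Activities are rated by participant from 1 (not at all) to 5 (extremely"). It states that the summed score lies on a scale from 0 to 60 and continues: "This score is then divided by 60 and multiplied by 100 to get a score between 0 and 100". A form with at least 6 but fewer than 12 items is valid, and for it "their total score is divided by the maximum score for the items completed and multiplied by 100".

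Protocol 15.2.5 gives the same 1-to-5 coding, with items "summed to calculate a total score using a scale from 0 to 100", and no formula.

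The main SAP (3.2.2 and 9.6) sets a responder threshold of 8 points, with 7 and 9 also presented. SAP 9.6 adds: "A 7 point change in MSWS-12 is considered clinically meaningful". It does not say on which scale those points are counted.

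SAP Appendix I, section 5.2, repeats the 0-60 raw range and drops raw-score tabulations because the literature uses a 0-100 scale. It then says: "MSWS-12 on scores mapped to a 0-100 scale will be summarized for following point improvement", naming 10, 15 and 20 points and referring to publications in general. On raw data it says: "The raw scores will be included in the data listings". It gives no replacement formula and does not say whether the 7/8/9 thresholds are kept.

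**The concern.** Items that start at 1 cannot sum to 0. Dividing the sum by its maximum without first subtracting its minimum leaves a floor above zero, so the range stated in SAP 9.6 does not follow from its own formula. A participant who answers at the lowest level on all 12 items scores 20.

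Appendix I makes this matter more. The rescaled score is now the only one tabulated, and its responder thresholds are chosen on a 0-100 metric. If the formula is programmed as written, tables labelled 0-100 would show changes and responder rates on a compressed scale. To the extent that the publications behind the thresholds use a true 0-100 score, the results would not be comparable with them. The study's stated purpose is to inform the design of a later randomized study, so a mean change, SD or responder rate carried forward on the wrong scale could mislead that planning.

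**Working it through.** **Inputs.** 12 items, each coded 1 to 5; score = sum/60 × 100; for k completed items (6 to 11), score = sum/(5k) × 100 (all SAP 9.6). Thresholds are 10/15/20 (Appendix I, 5.2) and 7/8/9 (SAP 3.2.2 and 9.6).

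**Range as written.** The minimum sum is 12 × 1 = 12 and the maximum is 12 × 5 = 60. The formula gives 12/60 × 100 = 20 up to 60/60 × 100 = 100, so the stated 0 to 100 is not reproduced. For k items the minimum is k/(5k) × 100 = 20, the same floor. Two other codings were tried. Items coded 0 to 4 with division by 60 give 0 to 80. Items coded 0 to 5 give 0 to 100 but contradict the stated 1-to-5 coding.

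**Relation to a true 0-100 score.** Put P = 100(s − k)/(4k), which runs from 0 to 100. Then 100s/(5k) = 20 + 0.8 × P for every k from 6 to 12 and every possible sum s. On a complete form one raw point is worth 100/60 = 1.667 points as written against 100/48 = 2.083, a ratio of 0.80.

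**Responder bars, all 12 items complete.** The raw points needed are the next whole number at or above 0.60t as written, and at or above 0.48t on the 0-100 score.

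| Threshold t | As written | 0-100 score | Rise in whole points |
|---|---|---|---|
| 7 | 4.2 → 5 | 3.36 → 4 | 25% |
| 8 | 4.8 → 5 | 3.84 → 4 | 25% |
| 9 | 5.4 → 6 | 4.32 → 5 | 20% |
| 10 | 6.0 → 6 | 4.8 → 5 | 20% |
| 15 | 9.0 → 9 | 7.2 → 8 | 12.5% |
| 20 | 12.0 → 12 | 9.6 → 10 | 20% |

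Before rounding, every bar is 25% higher (0.60/0.48 = 1.25). As written, the 10/15/20 bars equal 12.5, 18.75 and 25 points on the 0-100 score. The rows for 7/8/9 assume that those thresholds are also meant as 0-100 points. On complete forms, participants improving by exactly 5, 8, or 10 to 11 raw points change status at the 10-, 15- and 20-point bars respectively; for 7 and 8 it is those improving by exactly 4, and for 9 by exactly 5. The table also shows that ≥7 and ≥8 are the same test under either formula, as are ≥9 and ≥10.

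**Partly completed forms** (same number of items at both visits). The whole-point rise for the 10/15/20 bars varies from 0% (10-point bar: 3 vs 3 with 6 items, 4 vs 4 with 8) to 33% (10-point bar with 7 items, 4 vs 3; 15-point bar with 10 items, 8 vs 6).

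**Percent change.** For baseline raw sum b and raw change d, the SAP formula gives d/b and the 0-100 score gives d/(b − 12), so the ratio is (b − 12)/b. At b = 24, 36 and 48 it is 0.50, 0.67 and 0.75. For example, a 6-point raw fall from 36 is −16.7% as written and −25% on the 0-100 score.

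**Illustrative responder rates.** The documents give no MSWS-12 mean or SD, so these are assumed. With P(raw improvement ≥ r) = 1 − Φ((r − 0.5 − mean)/SD), mean 2 and SD 6:

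- ≥10: 1 − Φ(2.5/6) = 33.8% falls to 1 − Φ(3.5/6) = 28.0%
- ≥15: 1 − Φ(5.5/6) = 18.0% falls to 1 − Φ(6.5/6) = 13.9%
- ≥20: 1 − Φ(7.5/6) = 10.6% falls to 1 − Φ(9.5/6) = 5.7%

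Over means 0, 2, 4, 6 and SDs 4, 6, 8, the loss runs from 0.7 to 10.6 percentage points, or 0.1 to 2.1 of 20 participants.

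**The case against.** The strongest reply is that little is lost. The error is a fixed linear rescaling of an endpoint that Protocol 9.3.4 calls supportive, in a 20-person study with no sample size calculation. Raw scores are listed. A test of mean change from baseline gives the same t statistic and p-value on either scale. The responder error can only run downward, which is conservative. Appendix I, section 5, names T25FW, 9-HPT and MRI as the registry data, not MSWS-12, so no historical MSWS-12 comparison is shown to be at risk. The team also plainly intends a 0-100 score, and the program cannot be seen; it may already be right.

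All of this is fair, and it limits the severity. It does not remove the error: percent changes and responder counts are not invariant to the shift, and the written formula is the only one in the documents.

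Three further cautions also stand. Appendix I names no particular publication, so a mismatch with published results is conditional. The 12.5% to 20% rise applies to complete forms only. The assumed means cover no change or improvement, although the protocol's introduction describes gradual worsening in progressive MS. At mean −2 and SD 4 the loss at the 20-point bar is only about 0.2 percentage points, so the range above is illustrative and not a bound.

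**Conclusion.** The formula is wrong as written and should be corrected. The range error (20 to 100) and the shrinkage of changes to 80% are exact and rest only on the SAP's own text. So does the rise in the 10/15/20 bars on complete forms, by 20%, 12.5% and 20% in whole raw points. The effect on results arises only if the formula is programmed as written. The number of responders lost depends on data not in the documents; about one in 20 is a plausible illustration. Mean changes and their SDs can be converted by multiplying by 1.25. Percent changes and responder counts must be rederived from the scores. The safety endpoint and the T25FW/9-HPT endpoint are unaffected.

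**What to change.** - In SAP 9.6, define the score as (sum − k)/(4k) × 100 for k ≥ 6 completed items, which is (sum − 12)/48 × 100 for a complete form. Give the raw range as 12 to 60 there and in Appendix I.
- Apply every point threshold to this score. State in Appendix I on which scale 7, 8 and 9 are counted and whether they are kept.
- The corrected score can be 0 at baseline, which the present formula cannot produce. SAP 6.7.3 says "If baseline is 0, change from baseline is defined as missing", and read literally this would drop such a participant's absolute change as well. Amend it so that a baseline of 0 makes only the percent change missing. The clause is needed for MSWS-12; the same wording already reaches other scores that can be 0, such as LCLA (0 to 70), so a general correction would be tidier.

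The cost is one derivation line in the SAP and the derived dataset, one clause in 6.7.3 and one sentence in Appendix I. No new data are needed.

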5.2 Actigraph

Summary and Analysis of Change and % Change from Baseline in Daily Step Count following Timed-25 Foot Walking (T25FW) will be excluded from the analyses as data is not available and this cannot be analyzed.

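### SAP 9.6 accepts a wearable day on hours worn but scales it by hours worn awake, so the scaling factor for daily step count has no upper limit

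*SAP*

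**What the plan says.** The rules are in SAP 9.6, under physical activity measured by the wrist sensor.

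- **Valid day:** "A daily assessment will be considered valid if the device was worn for at least 4 hours". Nothing limits this to waking hours.
- **Scaling:** the next sentence takes the activity on a valid day and scales it by "dividing it by the number of hours the device was worn while awake and multiplying it by 16 (average waking period").
- **Night wear:** "Subjects have the option to either take it off while they sleep or keep it on".
- **Averaging:** "Baseline will be the average of valid data from up to 7 days prior to the first treatment (V3"), leaving out the treatment day. Post-treatment values are the "average of valid data from each 7-day interval following each treatment visit". Neither window has a minimum number of valid days.
- **Outliers:** "Due to outliers, analyses may be performed including and excluding outliers". No outlier is defined and no limit is put on the scaling factor.

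The later appendix to the SAP changes one thing for this device (its section 5.2 Actigraph): the analysis of "Change from Baseline in Daily Step Count following Timed-25 Foot Walking (T25FW) will be excluded from the analyses". The validity and scaling rules stand.

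Protocol 1.1.2 and 9.2.5 and SAP 3.1.2 and 3.2.2 list daily step count under the secondary objectives and endpoints. SAP 3.2.2 reports it as mean change and mean percentage change.

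**The concern.** Two consecutive sentences use different quantities. The first decides whether a day has enough data, and on its plain wording it counts all wear. The second decides how far the day is extrapolated, and it counts awake wear only. When the device stays on overnight, the first quantity can be large while the second is close to zero. The validity test then fails to do its job, which is to keep out days with too little waking data to scale.

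At stake is the precision, and possibly the accuracy, of the step-count summaries. The study has 20 participants and no concurrent control. Each weekly value is an arithmetic mean of at most seven scaled days, so one unstable day carries at least one seventh of the weight, and all of it if it is the only valid day.

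**Working it through.** The documents give no scaling factor or worked example, so there is no stated figure to reproduce. The factor follows from the rule itself.

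**Step 1. The factor.** Scaled value = recorded activity / h × 16, where h is hours worn while awake. The factor is therefore 16/h.

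| Awake hours worn (h) | 16/h |
|---|---|
| 0 | undefined |
| 0.25 | 64 |
| 0.5 | 32 |
| 1 | 16 |
| 2 | 8 |
| 4 | 4 |
| 8 | 2 |
| 16 | 1 |

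As written, every row can be a valid day if sleep wear brings total wear to 4 hours. For example, 8 hours asleep plus 0.5 hours awake (assumed) is 8.5 hours worn: valid, with a factor of 32.

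**Step 2. What one such day does to a weekly value.** Assumed figures, none from the documents: a participant's usual scaled level is 3,000 steps a day, and one day has 0.5 awake hours worn. The usual rate is 3,000/16 = 187.5 steps an hour, or about 94 steps in half an hour.

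| Steps in the half hour | Scaled day (× 32) | 7-day mean, other six days at 3,000 | Shift in the mean of 20 participants | Same shift if it is the only valid day |
|---|---|---|---|---|
| 0 | 0 | 18,000/7 = 2,571 | −21 | −150 |
| 100 | 3,200 | 21,200/7 = 3,029 | +1 | +10 |
| 300 | 9,600 | 27,600/7 = 3,943 | +47 | +330 |
| 600 | 19,200 | 37,200/7 = 5,314 | +116 | +810 |

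The last two columns are (weekly value − 3,000)/20, with the weekly value equal to the scaled day in the final column.

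The 100-step row matters. Half an hour close to the usual rate scales to close to the usual level. A large factor is not an error in itself. It magnifies any departure of the worn period from the rest of the day, upward or downward.

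**Step 3. How the floor changes this.** Each extra recorded step adds 16/h scaled steps. A burst of 200 extra steps (assumed) adds 200 × 32 = 6,400 at 0.5 awake hours. At exactly 4 awake hours it adds 200 × 4 = 800. Floors of 8, 10 and 12 awake hours have largest factors of 2, 1.6 and 1.33, so the same burst adds at most 400, 320 and 267.

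**Step 4. An unstated numerator.** The SAP does not say whether the activity being scaled excludes movement during sleep. Suppose it does not, and sleep movement runs at a fraction a of the waking rate over 8 hours (assumed). The half-hour day then scales to (8a + 0.5) × 32/16 times the true waking level: 1.16, 1.8 and 2.6 for a = 0.01, 0.05 and 0.10. A fully worn day gives (8a + 16)/16 = 1.005, 1.025 and 1.05. On that reading the sparse day is biased upward as well as noisy.

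**The case against.** **The 4 hours may have been meant as awake hours.** This is possible, and the factor would then never exceed 4. But the next sentence says awake and this one does not, so the plain reading is that they differ. If awake hours were meant, the wording should say so; that is the change proposed below.

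**The scenario runs against the wear instruction.** Protocol 4.3 and SAP 9.6 ask for wear throughout the study, and the only stated removal option is during sleep. Night-only wear reverses that pattern. This stands: such days are possible, but the documents give no ground for calling them common.

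**The plan has safeguards.** SAP 6.4 reports the median and quartiles, which resist one extreme participant, and SAP 9.6 foresees analyses without outliers. Both help in part. The listed endpoint is still the mean change, and each participant's weekly value is a mean before any median is taken. The outlier analysis is optional and undefined, so exclusions could be decided after the values have been seen.

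**Stronger readings a reader might infer.**
- *A 32-fold bias.* Not supported: 32 multiplies the recorded activity, and a typical half hour scales to about the right value.
- *All wearable measures are affected.* Not supported: counts per minute is already a rate, and the SAP does not explain how a multiplier of 16 would apply to it. The percentage of time above 100 counts per minute is a proportion. The effect is clear for daily step count only.
- *Four awake hours is too few, or ten is needed.* Nothing in the documents supports a particular floor. Objecting to a 4-fold extrapolation is a preference about thresholds; the mismatch between the two sentences is the defect.

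**Conclusion.** The point holds on the plain text. The validity test and the scaling denominator rest on different quantities, sleep wear can satisfy the first without adding to the second, and the factor for a valid day has no upper limit and no rule at zero awake hours. Neither the optional outlier analysis nor the SAP appendix repairs this.

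The consequence is extreme noise in daily step count on affected days, and distortion where the awake period is atypical or sleep movement is counted. In the assumed example, one half-hour day moves a participant's 7-day mean from 3,000 to between 2,571 and 5,314. The frequency of such days is unknown from the documents, so the overall effect on the endpoint cannot be sized here. The sponsor can count the days.

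This should be corrected, but it does not threaten the trial's main conclusions. The primary safety endpoint and the T25FW/9-HPT responder endpoint do not use these data, and the registry comparison in section 5 of the SAP appendix names T25FW, 9-HPT and MRI only.

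**What to change.** Amend SAP 9.6 so that the 4-hour minimum applies to hours worn while awake, the quantity already used for scaling. This caps the factor at 16/4 = 4 and removes the undefined case at zero. State in the same place whether the activity being scaled excludes movement during sleep.

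As sensitivity analyses, repeat the step-count summaries with higher awake-hour floors (for example 8, 10 and 12 hours, all assumed values) and with a stated minimum number of valid days in each 7-day average.

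The cost is a wording change and reprocessing of data already collected, with no new procedure for participants. Some days will become invalid, and some weekly values may be lost. Report how many days are lost at baseline and in each post-treatment week; this also shows how much the present rule mattered.
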